first 1 month before surgery Inflammatory drug or daily analgesic; (4) patients with diabetes history or blood glucose detection abnormal (fasting blood glucose $\geq 7\text{ mmol/L}$); (5) liver, renal function is abnormal (AST, Alt ≥ 1.5 times ULN, creatinine ≥ 1.5 times ULN); (6) has serious endocrine and metabolic diseases; (7) There are historical history of three high blood pressure; (8) History of osteoporosis; (9) History of autoimmune diseases; (10) Because of malignant tumors or other serious medical history, surgery should not be accepted or led to observation of teeth; (11) Pregnancy or lactating women; (12) Patients with anesthetic allergy; (13) Clinical or radiology shows that there are acute infections, root lesions, roots, severe eradications, dental bone rats, non-easy to abrasive, and osteoplasses (CEJ) or There is no treatment of untreated bilrels in the roots, the repair body is gains and / or in CEJ or the following repair edges are not in close; (14) A subject that can cause oral imaging inspection artifacts, such as: The study of teeth and its neighboring teeth are metal dentures, porcelain teeth; (15) a patient with root-stricken lesions;

3. Diagnostic criteria

(1) . Periodontal pocket $> 3\text{ mm}$, and inflammation, gingival bleeding (2) . Adjacent clinical attachment loss $> 1\text{ mm}$ (3) . Periodontal pocket bleeding on probing (4) . Alveolar bone has horizontal or vertical resorption. The progress of the disease is slow, and the teeth are loosened or displaced in the late stage.

4. Criteria for withdrawing / terminating tests

(1) . Any unexpected time to break blindness (2) . Patients who were found to be sensitive to or rejected implants during / after operation. (3) . Problems in need of treatment that met the exclusion criteria. (4) . Patients with irresistible factors such as non-migration / death lost follow-up during the study period.

VI. Research methods

1. Randomized controlled scheme

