A simple random method is used for random grouping. The specific method is as follows: first, a column number 1x 78 is established by Excel2013, and then the random number between 0 and 1 is generated by the other column, and then sorted by the largest to the smallest. The first 26 numbers are assigned to the GTR group, the middle 26 numbers are assigned to the APRF+GTR group, and the last 26 numbers are assigned to the CGF+GTR group. The subjects were divided into GTR group, APRF+GTR group and CGF+GTR group according to 1:1:1. (2) researcher A put the implant name (APRF or CGF or none) corresponding to the group mark into 78 Kraft paper envelopes with serial number 1: 78 and opaque according to the distribution order list. A gave the sealed envelope to B and no longer participated in the follow-up study. Researcher B is responsible for including the subjects according to the inclusion criteria, assigning the tested according to the order of seeing a doctor, and is responsible for supervising the operation process.

2. Blind design

Researcher A put the name of the implant corresponding to the group mark (APRF or CGF or none) into 78 Kraft paper envelopes with serial number 1x78 and opaque according to the assigned order list. A gave the sealed envelope to B and no longer participated in the follow-up study. Researcher B is responsible for including the subjects according to the inclusion criteria and assigning the number of the subjects according to the order of seeing a doctor. During the operation, researcher B will hand over the sealed envelope to the surgeon according to the number, supervise the operation process, and do not participate in other studies such as measurement. The survey researcher is responsible for measuring various indicators on a regular basis. Until the end of the experiment, the measurement researchers did not know how the subjects were grouped.

3. Treatment scheme

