The newly diagnosed patients were recalled after 6-8 weeks of basic treatment to evaluate whether they met the inclusion exclusion criteria and confirm the operation site. For the patients considering inclusion, they agreed on the operation time one week later (female patients avoided menstruation). Oral health education was given to the patients again. One week later, the operative (V0), the informed consent form was signed by the patient, and then the researchers measured the baseline of the included patients, including (1) clinical periodontal index: probing depth (PD), clinical attachment level (CAL), mobility

(mobility), probing bleeding (BOP). (2) Imaging examination: the height of bone defect (IC), bone level (RBL) and the angle of intraosseous defect were measured by CBCT image, and the volume of intraosseous defect was measured after three-dimensional reconstruction of the affected teeth: all measurements were repeated twice to take the average value; before the actual measurement, all measurement researchers have passed the consistency test. Researcher A uses a random number table for random grouping and uses opaque sealed envelopes for distribution and concealment, and then hands over the envelopes to researcher B and no longer participates in the follow-up study. Researcher B numbered the enrolled patients 1-78 in order. Before the operation, researcher B handed over the sealed envelope to the itinerant nurse to open it, and both the patient and the patient were blind at this time. Since then, researcher B is responsible for supervising the operation. All the operations were performed by experienced surgeons. The surgical area was anesthetized before operation, intraoral and perioral routine disinfection was performed, and the operation was carried out in accordance with the principles of routine periodontal regeneration and aseptic operation.

If the patient was assigned to the APRF+GTR group, 20ml was collected with a blood collection needle from the superficial elbow vein immediately before operation and placed in two special glass centrifuges for APRF. Immediately after the blood collection was completed, the blood was symmetrically placed in the TR-18plu series centrifuge, and the 14min was centrifuged with 1500rpm at room

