temperature. After centrifugation, the intravascular blood was divided into three layers: the upper layer was PPP, the middle was yellowish cylindrical gel-like APRF, and the bottom layer was erythrocyte layer. The 2 test tubes completed by centrifugation were placed vertically on the operating compartment table for backup (not tilted or inverted). Simplified gingival papilla retained incision cut full thickness flap and fully relaxed incision and (the flap should be extended 1-2 teeth to the proximal and distal part of the tooth, if the adjacent tooth is missing, the incision should be extended at least 5-10 mm to the area of edentulous teeth). Thoroughly remove the root calculus, plaque and granulation in the defect area with a Gracey curette and spoon, expose the intraosseous defect, cut one piece of APRF gel into 1-2mm particles and mix with Bio-oss, and the other piece is pressed into a 1mm film with special equipment; trim the Bio-gide collagen membrane according to the shape of the bone defect, the membrane should cover the edge of the defect at least 2mm. The mixture of APRF and Bio-oss was filled into the bone defect, the Bio-gide membrane was trimmed, and then the APRF membrane was covered with it; the gingival flap was restored to close the window with improved cross-horizontal mattress suture; periodontal plug agents were placed in the operation area.

If the patient was assigned to the CGF+GTR group, the patient immediately used a blood collection needle from the superficial elbow vein to collect blood about 20ml, which was placed in two special CGF centrifuges with silica coating on the inner wall of the centrifugal tube. Immediately after the blood collection

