was completed, the symmetrical Medifuge centrifuge was selected, and the CGF procedure was selected and centrifuged for 13 minutes. The CGF centrifugation procedure is as follows: accelerate for 30 seconds, rise to 2700r/min, centrifuge for 2 minutes, then descend to 2400r/min, centrifuge for 4 minutes, accelerate to 2700r/min, centrifuge for 4 minutes, then descend to 3000r/min, centrifuge for 3 minutes, and decelerate to stop in the last 36 seconds. Finally, the blood in the test tube is divided into three layers: the top layer is PPP, the lowest layer is crimson jelly-like red blood cells and platelets, and the middle layer is yellow translucent gel-like CGF. The 2 test tubes completed by centrifugation were placed vertically on the operating compartment table for backup (not tilted or inverted). The APRF gel in the above process was changed to CGF gel, mixed and covered with CGF, and the other operations were the same.

If the patient was assigned to the GTR group, no blood was drawn. Gel or membrane containing growth factor was not used to cover the operation, and the rest of the operation was the same.

At the end of the operation, the surgeon gave the patient postoperative medical advice and given postoperative medication: cefuroxime axetil 50mg, ornidazole 500mg, twice a day for 5-7 days. Oral hygiene education was given to the patients again, and patients were advised to use Koutai mouthwash twice a day for 2 weeks, and about 2 weeks later to remove stitches. Two weeks after operation, stitches were removed by the original surgeon, and the patients were scheduled for 12 weeks \pm 7 days (V1), 24 weeks \pm 14 days (V2) and 48 weeks \pm 28

days (V3).

VII. Observation index and evaluation of curative effect

The patients were contacted and followed up by researcher B at 12, 24 and 48 weeks after operation. At 12 weeks \pm 7 days after operation, PD, CAL, mobility and BOP were measured by measurement researchers. 24 weeks \pm 14 days and 48 weeks \pm 28 days after operation, the researchers measured PD, CAL, mobility, BOP, RBL, IC, intraosseous defect angle and bone defect volume.

PD (probe depth) :use a periodontal probe (UNC-15,Hu-Friedy,Chicago,IL) paralleling to the long axis of the tooth to measure the distance from the bottom of the periodontal pocket to the gingival margin (mm), record six sites of each tooth (the mesial, median and distal site of the buccal and tongue surface).

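### Sections VI.2 and VI.3 disagree on who receives the envelope and when, and the surgeon can know concentrate versus GTR before debridement

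*Combined protocol and SAP*

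**What the plan says.** **Envelope, first account.** Section VI.2 (Blind design): "During the operation, researcher B will hand over the sealed envelope to the surgeon according to the number". It does not say who opens the envelope.

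**Envelope, second account.** Section VI.3 (Treatment scheme): "Before the operation, researcher B handed over the sealed envelope to the itinerant nurse to open it". The text continues that "both the patient and the patient were blind at this time". That sentence names the patient twice, so the second party is unclear.

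**Blood draw.** Section VI.3, APRF arm: "20ml was collected with a blood collection needle from the superficial elbow vein immediately before operation". The CGF arm also gives about 20 ml, into silica-coated tubes. For the control arm: "If the patient was assigned to the GTR group, no blood was drawn". No sham draw is described.

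**Tubes.** For APRF, and again in the same words for CGF: "The 2 test tubes completed by centrifugation were placed vertically on the operating compartment table for backup". In the APRF text this comes before the incision, the flap and the clearing of the defect.

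**Assessors.** Section VI.2: "Until the end of the experiment, the measurement researchers did not know how the subjects were grouped". Researcher B, who handles the envelopes and supervises surgery, takes no part in measurement.

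**Withdrawal.** Section V.4 lists "Any unexpected time to break blindness" as a criterion for withdrawal or termination, without saying whose blinding is meant.

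**The concern.** Flap design and debridement are meant to be the same in all three arms, and both depend on the operator. A surgeon who already knows the arm could carry them out differently, and any resulting difference in healing would be counted as an effect of the concentrate. This exposure is partly avoidable: the surgeon must learn the arm to place the graft, but need not know it before the defect is exposed.

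The second route runs through the patient. PD, CAL, mobility and BOP are taken by hand at 12, 24 and 48 weeks. A patient who mentions having had, or not having had, blood taken tells the measuring researcher whether a concentrate was used. Blinding of that researcher is the one lasting protection the plan states.

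The conflict between VI.2 and VI.3 also matters by itself, because theatre staff cannot follow both.

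**Working it through.** The plan gives no figure on this point, so the check is mainly one of order and consistency.

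**1. The two accounts side by side**

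| | VI.2 | VI.3 |
|---|---|---|
| Who receives the envelope | Surgeon | Circulating (itinerant) nurse |
| When | During the operation | Before the operation |
| Who opens it | Not stated | The nurse |

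Recipient and timing both differ.

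**2. Does the VI.2 timing fit the blood draw?** In the APRF arm blood is taken immediately before the operation and spun for 14 minutes. The draw is made only if the patient is in that arm, so someone must know the allocation before surgery starts. A first disclosure during surgery therefore does not fit. The CGF arm also needs a draw and a 13-minute spin, but its text does not tie the draw to a time before the operation, so the conflict is explicit for APRF only.

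**3. When can the surgeon know?** Order in VI.3: baseline measured; envelope opened; blood drawn and spun (two arms); tubes placed on the operating table; incision and flap; debridement and defect exposure; graft and membranes placed. The tubes come before the three-arm common steps. Tubes present means a concentrate arm, and tubes absent means GTR. No screening, covering or delayed disclosure is described.

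**4. What does the draw reveal?** Allocation is 26 + 26 + 26 = 78 (section VI.1), which agrees with the 78 envelopes. Chance of naming the arm correctly:

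- no information: 1/3;
- draw or no draw seen: (26 × 1 + 52 × 0.5) / 78 = 52/78 = 2/3;
- tube, centrifuge or product type also recognised: 1.

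The draw identifies GTR fully. It does not separate APRF from CGF, because both give about 20 ml.

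**5. Size of any bias.** The documents give nothing from which to estimate it. Purely as an assumption, suppose that knowledge of the arm shifts both concentrate arms by *d* SD and that there is no true effect. One-way ANOVA with 26 per arm has 2 and 75 degrees of freedom and noncentrality 26 × (2/3) × *d*².

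| Assumed *d* | Noncentrality | False-positive rate at 0.05 |
|---|---|---|
| 0.1 | 0.17 | 6.3% |
| 0.2 | 0.69 | 10.4% |
| 0.3 | 1.56 | 17.8% |

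This shows how sensitive the test would be to such a shift. It is not evidence that one occurs.

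**The case against.** **The plan does not promise what the draw takes away.** A reader might infer that it claims patient and surgeon blinding which the draw and the tubes then destroy. The documents do not support that. The only patient-blinding sentence is garbled, is limited to the moment of envelope opening, and does not name the surgeon. The only lasting claim concerns the measurement researchers. The withdrawal criterion on broken blinding hints at something that continues, but does not say for whom. This objection stands.

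**VI.2 may be loose translation.** It describes a handover, not an opening, and the word for operation could mean the whole session. That could soften the timing conflict. It does not explain a different recipient, and the passages still need reconciling.

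**There are safeguards.** One surgical procedure is described for all arms, the surgeons are experienced, and researcher B supervises and does not measure. These reduce the risk of different debridement, which remains a possibility and not a finding. They do not keep the arm from the surgeon.

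**Patient disclosure has limited reach.** The first follow-up measurement is at 12 weeks. IC, RBL, defect angle and volume come from CBCT, and a patient's remark need not reach the image reader. APRF versus CGF is largely untouched by what the patient can infer. All of this stands, and it confines the patient route mainly to hand-measured outcomes in the comparisons with GTR.

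**Covering the tubes would not be enough.** GTR has neither tubes nor a spin, so covered tubes on the table, or a wait before incision, would still give the arm away. This is right, and the fix below allows for it.

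**Conclusion.** The point holds in a limited form. Sections VI.2 and VI.3 conflict on recipient and timing, and the VI.2 timing does not fit the APRF draw. Separately, the order of events in VI.3 lets the surgeon know concentrate versus GTR during steps common to all arms. It also lets patients infer that same contrast, with no stated step to stop them passing it to the measuring researcher.

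It does not follow that concealment before enrolment failed, that assessor blinding is contradicted (it is stated, but not protected against patient disclosure), or that outcomes are biased. The 2/3 figure rests on the 26/26/26 allocation and on an observer who sees only whether blood was drawn. The size of any bias is unknown. This should be corrected, but it does not invalidate the design.

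**What to change.** - Make VI.2 match VI.3: the circulating nurse opens the envelope, after baseline has been recorded.
- In all arms, keep blood collection, tubes and centrifuge out of the surgeon's view and off the operating table. Keep the surgeon out of the room until surgery starts, so that neither tubes nor waiting time shows the arm.
- Disclose the arm to the surgeon only when debridement and defect exposure are complete.
- State that the trial is assessor-blind, and repair the garbled sentence in VI.3.
- State that the withdrawal criterion on broken blinding in V.4 does not apply to a patient who infers the arm from the draw.
- Ask patients not to mention the draw to the measuring researcher, and read CBCT images under a code.

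The cost is protocol wording, a small change of theatre routine and slightly more work for existing staff. Visits and sample size do not change. Masking of the surgeon before debridement may still be imperfect.

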This study is a single-center, simple random parallel group design clinical trial, each random group is allocated according to the proportion of 1:1:1.

IV. Clinical trial site

Responsibilities: Second Affiliated Hospital of Zhejiang University; [name];
[contact];

Address: [name]
Province; [name]

Participation Unit: the Second Affiliated Hospital of Zhejiang University Medical College; person in charge: [name]

V. Design of research

1. Inclusion criteria

(1) Age 18-80 years old; (2) a teeth choice: 6-8 weeks after the teeth after the periodic treatment of teeth, there is at least one site periodontal diagnosis depth (PD) ≥ 5 mm, looseness is less than II The degree or II-III degree will be loose after a fixed fixed, imaging evaluation of the vertical bone absorption of the teeth is greater than 3 mm osteogenesis, and the site is free of teeth surgical treatment, the patient has no obvious symptoms; (3) Patients have better compliance, and the bacterial plaque control is good after the basic treatment (all-in-law bleeding index and the mushroom index), can understand the purpose of testing, willing to cooperate with surgery and follow-up, voluntarily participate in the test and signed Informed consent.

2. Exclusion criteria

(1) In the past 6 months, chewing smokeless tobacco, smoking or suction cigar once a week or more, or smoking more than 20 / week (1 pack / week); (2) patients before blood Three months taking any drug or platelet counts that affect platelet function less than 200,000 / mm³; (3) patients have taken anti-epileptic drugs, antiplasia, antidepressants, sedatives, califiers, anti-depression, sedatives in the

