CAL (clinical attachment level) : The distance from periodontal pocket bottom to CEJ was measured by periodontal probe (mm). Record six sites of each tooth (the mesial, median and distal site of the buccal and tongue surface).

mobility: use a tweezer to clamp the incisal areas of the anterior teeth or the pit groove on the occlusal surface of the posterior teeth and shake the teeth faciolingually, mesiodistally and vertically. I degree : abnormal mobility faciolingually or less than 1mm positioning. II degree : abnormal mobility faciolingually and mesiodistally or loosening range of 1-2mm. III degree : abnormal mobility faciolingually, mesiodistally and vertically or loosening range is

greater than 2mm.

BOP(bleeding of probe) : observe for 10-15 seconds after probe to see whether it bleeds. Record six sites of each tooth (the mesial, median and distal site of the buccal and tongue surface).

RBL(radiographic bone level): Locate the reference point at the deepest PD site of the affected tooth: cemento-enamel junction (CEJ), alveolar crest (AC), bone defect (BD) .RBL is the straight line distance from CEJ to BD (mm)

IC: IC is the straight line distance from AC to BD (mm)

regenerated bone volume parameters : in mimics software, threshold was set according to the gray value of the affected tooth and its surrounding alveolar bone, image editing and region growth were used to form a mask of the three-dimensional reconstruction area. The three-dimensional calculation function was used to reconstruct the three-dimensional shape of the alveolar bone in the target area. Furthermore, the structure of alveolar bone was optimized by remeshing and smooth. The volume of alveolar bone before and after operation was calculated by Boolean operation to obtain the model of regenerated alveolar bone and its volume was measured.

Defect fill (%) = (preoperative IC- and postoperative IC) / preoperative IC × 100%

Defect resolution (%) = (preoperative RBL- and postoperative RBL) / preoperative RBL × 100%

VIII. Statistical analysis method (statistical software: SPSS25.0)

1) data description: measurement data are described by mean \pm standard

deviation, non-normal distribution data are described by median and percentage (25th 75th percentile)

(2) baseline data are compared with normal distribution by one-way ANOVA test, while measurement data of non-normal distribution are described by Wilcoxon rank sum test.

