(3) to compare the curative effect, first of all, the normality and homogeneity of variance of the experimental data were tested. If it obeys normality and homogeneity of variance, one-way analysis of variance (One-Way ANOVA) is used to compare the differences of mean among groups. If there were significant differences, pairwise comparisons were made, and multiple comparisons were made with SNK-q test to analyze and compare the differences between groups. If it does not obey normality and homogeneity of variance, Friedman test is used to compare the mean difference of each group; if there is significant difference, pairwise comparison is made by Wilcoxon Matched-Pairs Sighed Rank test. $P < 0.05$ was used as an index of statistical difference.

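### Section VIII(3) routes bleeding on probing and mobility to matched-sample tests although the three arms are independent, and bleeding has neither a per-patient unit nor a method for yes/no data

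*Combined protocol and SAP*

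**What the plan says.** Section III describes a "simple random parallel group design clinical trial, each random group is allocated according to the proportion of 1:1:1", and section VI.1 assigns 26 numbers to each of three groups, 78 in all. No matching of patients across groups is described.

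Section VII states that "PD, CAL, mobility and BOP were measured by measurement researchers" at 12 weeks, and lists the same four indices again at 24 and 48 weeks. BOP is a yes/no reading: "observe for 10-15 seconds after probe to see whether it bleeds". The instruction for sites is "Record six sites of each tooth (the mesial, median and distal site of the buccal and tongue surface". Nothing says how six readings become one value per tooth or patient. Mobility is graded in ordered steps, for example "I degree : abnormal mobility faciolingually or less than 1mm positioning" and "II degree : abnormal mobility faciolingually and mesiodistally or loosening range of 1-2mm".

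Section VIII(3) gives one rule for comparing efficacy. Data that are normal with equal variances go to one-way ANOVA and SNK-q. For the rest: "If it does not obey normality and homogeneity of variance, Friedman test is used to compare the mean difference of each group", with Wilcoxon matched-pairs signed-rank tests for pairs of groups. The only independent-sample rank test, the Wilcoxon rank sum in VIII(2), is for baseline measurement data and compares two samples. No method for binary, ordinal or clustered data is named. The data description covers means and medians with their spread, but no counts or proportions.

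**The concern.** There are two separate faults.

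- **Wrong family of tests.** Friedman and signed-rank tests compare values within matched sets. Here row 1 of one arm has nothing to do with row 1 of another. Someone must invent the pairing, the p-value depends on it, and patients without partners are dropped when arms end at different sizes.
- **No unit or method for BOP.** Exchanging Friedman for an independent-groups rank test would be enough for mobility. BOP would still be six correlated yes/no values per tooth with no prespecified summary. The analyst would have to choose one after seeing the data, and one obvious choice, treating sites as independent, is invalid.

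At stake is the credibility of two of the four clinical indices measured at every follow-up visit.

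**Working it through.** The documents give no effect size, event rate, dropout or power, so there is no stated figure to reproduce beyond 3 × 26 = 78, which agrees. From the documents: 26 per arm, six sites, alpha 0.05. All rates, missingness and correlations below are assumptions. Simulations used at least 4,000 trials per setting for power and pooled-site error.

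**1. Which branch applies?** The plan does not name its normality test; Shapiro-Wilk is assumed. With mobility probabilities for grades 0/I/II/III of 0.30/0.40/0.20/0.10 in one arm and either the same or 0.55/0.30/0.10/0.05 in the other two, all three arms passed in 0% of trials. For a count of bleeding sites out of six (site rate 30% in every arm, or 45/25/25%), all three passed in at most 0.25%. Both outcomes therefore go to the matched-sample branch almost every time.

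**2. Does the pairing matter?** Shuffling the rows of the same mobility data changed the Friedman verdict at 0.05 in 14% of trials with the assumed effect, and in 3.7% with none. With arms of 26, 24 and 25 the test could not be computed at all.

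**3. Type I error.** Friedman with arbitrary pairing stayed at about 4.3–5.8%.

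**4. Power for one yes/no BOP value per patient, at 60/25/25%.** Closed-form check for chi-square with complete data: mean rate = (0.60 + 0.25 + 0.25)/3 = 0.3667. Noncentrality = 26 × [(0.60 − 0.3667)² + 2 × (0.25 − 0.3667)²] / (0.3667 × 0.6333) = 26 × 0.0817/0.2322 = 9.14. On 2 df with critical value 5.99, power is 78%, which matches the simulation.

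The table gives ranges over repeat simulations. Losses are taken within a run.

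| Missing | Chi-square | Friedman, available patients lined up | Friedman, triplets fixed before dropout | Loss (points) |
|---|---|---|---|---|
| 0% | 78% | 77% | 77% | about 1 |
| 10% | 73–75% | 69–71% | 61–63% | about 4 to 12 |
| 15% | 71–73% | 66–68% | 54–56% | about 5 to 17 |

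Complete fixed triplets: 0.90³ = 73% and 0.85³ = 61%. Lining up the available patients keeps about 85% and 79% of rows.

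**5. Other summaries, complete data.** For the six-site count at 45/25/25%, Kruskal-Wallis against Friedman has power 87% v 81%, 77% v 69% and 59% v 52% at within-tooth correlation 0.1, 0.2 and 0.4. For mobility, with the effect in step 1, it is 49% v 45%.

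**6. What if sites were pooled as independent?** The design effect is 1 + (6 − 1) × ρ. A 2-df chi-square then rejects wrongly at about 0.05^(1/design effect):

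- ρ = 0.1: 0.05^(1/1.5) = 13.6%
- ρ = 0.2: 0.05^(1/2) = 22.4%
- ρ = 0.3: 0.05^(1/2.5) = 30.2%
- ρ = 0.4: 0.05^(1/3) = 36.8%

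Simulation at a 30% site rate gave 13%, 21%, 30% and 38%.

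**The case against.** **The matched-test error is not specific to these outcomes.** This stands. It reaches every outcome that fails the check, including probing depth, attachment level and the imaging measures, and should be corrected once for all. Probing depth and attachment level also carry the six-site instruction without a summary. What is particular to BOP is that the general correction still leaves it without a unit and without a binary method.

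**The loss may be small.** This stands in part. With complete data and one yes/no value per patient, Friedman costs about 1 point. A reader might infer that power must fall to about 55–63%, but that needs triplets fixed before dropout, and the plan specifies no pairing. A reader might also infer false positives; Friedman does not produce them here.

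**Pooling is hypothetical.** This stands. Section VIII nowhere proposes treating sites as independent, so the 13–38% is a warning about one way of filling the gap, not a property of the plan.

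**A count could be analysed by ANOVA.** On a per-tooth BOP count, ANOVA had type I error of 4.5–4.9%. But the plan defines no such count, and its own normality rule would nearly always turn it away.

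**Splinting.** From the inclusion wording "looseness is less than II The degree or II-III degree will be loose after a fixed fixed" a reader might infer that splinted teeth blur the mobility comparison. The text is too garbled to carry this. Nothing says that mobility is graded with a splint in place or how many teeth would be affected, and restricting the analysis to unsplinted teeth would be a debatable subset. No such claim is made here.

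**Conclusion.** The point holds. For BOP and mobility the stated rule leads almost always to tests for matched data in a trial with none. The harm is an arbitrary result and discarded data, with a power loss that runs from about 1 point to about 17 under the assumed 60/25/25% rates, depending on missingness and on a pairing the plan leaves open. Separately, BOP lacks a defined per-patient value and any method for yes/no data, and correcting the rank test alone does not cure that. The existence of both faults rests on the text; only their size rests on assumed rates and correlations. Neither outcome is named as primary and the stated aim is alveolar bone regeneration, so this should be corrected but does not by itself undermine the trial's main question.

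**What to change.** Amend section VIII before any outcome data are examined:

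- **BOP:** choose one definition in advance. Either take bleeding at the index site fixed at baseline (section VII already uses the deepest probing site as the reference for bone level) and compare arms by chi-square or Fisher's exact test, or by logistic regression. Or take bleeding sites out of six and use logistic GEE clustered on patient.
- **Mobility:** Kruskal-Wallis with independent-sample pairwise rank tests, or proportional-odds regression with baseline grade.
- **Description:** counts and percentages by arm and visit for both.
- **General rule:** in the same edit, replace Friedman and matched-pairs signed-rank tests with independent-groups tests for all other non-normal outcomes.

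The cost is a few lines of text. All of these methods are available in SPSS 25, and no extra patients or measurements are needed. The index-site option is simpler but ignores the other five sites; GEE uses all six at the price of a model.
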